The reference range for the VerifyNow assay in individuals not on antiplatelet therapy is 180-376 PRU. These data are continuous and normally distributed. Thus, means and standard deviations will be used to describe reductions in platelet aggregation. Based on reported literature indicating additional effects of statins on platelet function following 30-day vs shorter periods of treatment, we have revised our experimental design to have a primary endpoint of 30-day treatment. Within-group thirty day evolocumab treatment will be tested by one-group paired t-test (two-sided) using each subject as its own control (evolocumab treatment vs vehicle pre-treatment control). Between-group thirty day evolocumab treatment will be tested by standard two-group t-test (two-sided, evolocumab vs vehicle control group run in parallel). The sample size estimates have been run using one-group, paired t-test published data. Using PRU mean difference = 102, SD = 54, power = 0.8 and alpha = 0.05, we estimate 6 subjects. Since the effects of statins on platelet aggregation may be mediated by both LDL-lowering and non-LDL-lowering mechanisms, we can calculate the sample size based on 50% reduced mean difference (PRU = 51). Then, we estimate 11 subjects. An equal number of subjects will be required for the placebo group run in parallel. Target enrollment will include all patients screened; we estimate that 10% may not be eligible based on exclusion criteria and/or may not return for scheduled blood draws. Thus, for 80% power, the target enrollment is 24 subjects over two years.

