Secondary measures – Secondary measures will include various cellular and circulating markers of platelet activation measured by flow cytometry or commercially-available enzyme-linked immunoassays (ELISAs). The target enrollment of 24 subjects should provide at least 80% power to detect differences between treatment groups based on data reported in the literature. For example, platelet P-selectin level measured by flow cytometry and reported as % positive cells (out of 50,000 cells counted) showed a mean reduction  $\pm$  SD of  $10.9 \pm 6.0$  (simvastatin),  $10.9 \pm 5.6$  (atorvastatin),  $7.2 \pm 6.8$  (fluvastatin) and  $9.0 \pm 6.8$  (pravastatin) following 30 days of statin treatment in hypercholesterolemic patients compared with untreated controls. In a separate study of stroke patients with hypercholesterolemia, platelet P-selectin showed a mean reduction of  $41 \pm 27\%$  positive cells in response to thrombin following 6 months of treatment with simvastatin compared to baseline measurements in the same subjects before statin treatment. An additional

effect of simvastatin treatment was observed for soluble P-selectin serum concentrations measured by ELISA. Soluble P-selectin showed a mean reduction of  $46.4 \pm 49$  ng/ml compared to baseline measurements in the same subjects before statin treatment. Other secondary measures include VerifyNow IIb/IIIa and VerifyNow Aspirin assays.

C. Study Design: Amgen will provide Evolocumab and placebo as open label. An independent biostatistician will generate a randomization table and provide it to Research Pharmacy of CUMC and Research Pharmacy will randomize the subjects accordingly. All patients recruited will start with placebo and blood and urine samples will be collected at day 7 and day 14. Then, the subjects will be randomized so that half will continue to receive placebo and half will receive Evolocumab via subcutaneous injection of 140 mg every 14 days. Blood and urine samples will be collected at day 21 and day 28. Then, all patients will receive Evolocumab 140 mg every 14 days and the treatment will continue.

Blood and urine samples will be collected following Evolocumab therapy at day 84 and 196 (Fig. 2). While every effort will be made to collect the blood and urine samples on the indicated time points, variation for the sample collection within 1-3 days at the indicated time point will be

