allowed. The power of this design is that we can compare any changes due to Evolocumab therapy relative to a placebo control.

Based on the power calculations as detailed above, recruitment of total 20 participants into this study will give ~80% power for statistical significance of 0.05. We target to recruit 24 subjects over 2 year period. However, we anticipate that some participants will drop out from the study and incomplete data will be obtained. We will continue to recruit the subjects until the complete data sets for 22 subjects are obtained. Incomplete data from the dropout may not be used unless data up to 28 days at least are collected.

D. Genotyping: rs3184504 genotyping will be performed using the genomic DNA samples

and rs3184504 specific PCR genotyping primers from Invitrogen.

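### The plan gives a before-after test and a randomised test of the same evolocumab effect without saying which decides, and it sizes the trial on the before-after test, which cannot separate drug from time

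*Combined protocol and SAP*

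**What the plan says.** Section B (Power Calculation), under the primary measure, lists two tests of the thirty-day effect in consecutive sentences:

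- Within the evolocumab arm: "Within-group thirty day evolocumab treatment will be tested by one-group paired t-test (two-sided) using each subject as its own control". The comparison is specified as "evolocumab treatment vs vehicle pre-treatment control".
- Between arms: "Between-group thirty day evolocumab treatment will be tested by standard two-group t-test (two-sided, evolocumab vs vehicle control group run in parallel").

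Neither is called primary, and no rule covers the case where they disagree. Section F (Analysis) states hypotheses but does not rank the tests. The sample size (6 subjects at 102 PRU, 11 at 51 PRU, SD 54, alpha 0.05, power 0.8) is computed for the paired test. The placebo group is then made the same size.

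Section C (Study Design) fixes the order of treatment: "All patients recruited will start with placebo and blood and urine samples will be collected at day 7 and day 14". After that, "the subjects will be randomized so that half will continue to receive placebo and half will receive Evolocumab". Samples follow at days 21 and 28, and then all patients receive evolocumab. Section C says the strength of this design is that "we can compare any changes due to Evolocumab therapy relative to a placebo control". It gives one significance level, 0.05, and about 80% power with 20 participants in total.

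**The concern.** No patient has drug before placebo. In the paired test the treatment contrast is therefore also a contrast between an earlier and a later period. A change in adherence to background lipid treatment, an effect of being in a study, or a drift in the assay would be credited to evolocumab if it moved the later readings in one direction. The parallel placebo arm measures exactly that movement, but the paired test does not use it.

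The paired test cannot be dismissed as a side analysis, because it is listed first and the 80% power claim is built on it. Followed as written, the trial could report a significant within-arm fall in platelet reactivity when the placebo arm had fallen just as much. The plan gives no rule saying that the randomised comparison takes precedence.

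**Working it through.** **Inputs from section B.** Mean difference 102 PRU, halved to 51; SD 54; two-sided alpha 0.05; power 0.8; 11 subjects per arm. **Assumed here:** the size of any time shift (the documents give none), and SD 54 for change in both arms.

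**1. The plan's own figure.** For a paired t-test the noncentrality is δ/SD × √n, referred to a noncentral t with n − 1 degrees of freedom.
- 51 PRU, n = 11: 51/54 × √11 = 3.13; critical value 2.228 (10 df); power 80.6%. With n = 10 it is 75.7%. The stated 11 reproduces.
- 102 PRU: n = 5 gives 87.8% and n = 6 gives 95.4%. The stated 6 is slightly generous.

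**2. Paired test with no drug effect and a time shift.** The formula is the same, with the shift in place of δ, n = 11.

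| Shift common to both arms (PRU) | Noncentrality | Paired test falsely positive | Two-group test |
|---|---|---|---|
| 0 | 0 | 5.0% | about 5% |
| 10 | 10/54 × √11 = 0.61 | 8.6% | about 5% |
| 20 | 20/54 × √11 = 1.23 | 20.0% | about 5% |
| 25.5 | 25.5/54 × √11 = 1.57 | 29.4% | about 5% |

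The value 25.5 is half of 51 and serves only as a reference point. The two-group rate does not move because a shift common to both arms cancels in the difference.

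**3. If either test could succeed, each at two-sided 0.05.** With no drug effect and no shift, simulation with 11 per arm gives about 8.3% to 8.4% when the two-group test compares changes. It gives about 9.2% to 9.6% when that test compares on-treatment values (pre/post correlation assumed between 0.3 and 0.7). Two independent tests would give 1 − 0.95² = 9.75%. These rates count significance in either direction. In the direction of benefit alone, the change-score version gives 4.2% against a nominal 2.5%.

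**4. Power of the randomised test at 51 PRU.** Noncentrality is δ/(SD × √(2/n)), with 2n − 2 degrees of freedom.
- 11 per arm: 51/(54 × √(2/11)) = 2.21; critical value 2.086; power 56%.
- 12 per arm: 51/(54 × √(2/12)) = 2.31; critical value 2.074; power 60%.
- 10 per arm (the 20 in section C): 51.5%; the paired test gives 75.7%.
- 19 per arm (38 in total): 81%, the first size above 80%.

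**5. Randomised window.** Patients are randomised after the day-14 sample, and all receive evolocumab after the day-28 sample. The text of section C therefore gives 28 − 14 = 14 days of parallel comparison, while section B labels the between-group test as thirty-day.

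**The case against.** The randomised test is already in the plan, the paired test is openly labelled as within-group, and section C presents placebo comparison as the strength of the design. A reader might infer that the sponsor means to claim efficacy from the paired test alone. No sentence says so. What the documents support is that the deciding test is not named.

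A reader might also infer that the plan runs two tests at 5% each and so has an inflated error rate. The documents do not establish this. The 0.05 in section B belongs to the sample-size calculation, section C gives a single 0.05, and no either-test rule is stated. The 8% to 10% is conditional on both assumptions.

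Nor do the documents show that any drift occurs. Several features limit it. Recruitment over two years spreads calendar-time assay drift across study phases. The baseline is taken on placebo after enrolment, so it already contains part of any participation effect. Entry depends on LDL cholesterol and platelet count rather than PRU, so patients are not selected on the outcome. These points reduce the bias but do not remove it, and the plan gives no evidence that the remainder is negligible.

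Finally, with a true 51 PRU effect and no shift, the paired test is significant and the randomised test is not in about 27% of simulated trials. It is tempting to read this as a further error rate. It is not: those paired results are true positives, and the disagreement mainly reflects the power gap of 81% against 56%. It does show that a rule for disagreement would be needed often.

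**Conclusion.** The concern holds in this form. One of two unranked tests of the drug effect is fully confounded with time, and it is the one that sets the sample size. That follows from the fixed placebo-then-drug order and needs no assumption about alpha or a decision rule.

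How much it matters depends on the time shift, which is unknown. At zero shift the paired test keeps its 5% level. The rates of 9%, 20% and 29% rest on assumed shifts of 10, 20 and 25.5 PRU, 11 subjects and SD 54. The power figures for the randomised test assume that SD 54, taken from a before-after comparison, also holds for change in each arm, and that the two-group test compares changes. Section B does not say whether it does.

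**What to change.** 1. In sections B and F, name the randomised evolocumab-versus-placebo comparison as the single primary test at two-sided 0.05, and state whether it compares changes or on-treatment values.
2. Report the change from the placebo run-in for both arms as supportive estimates with 95% confidence intervals, and state that no efficacy claim rests on them. Splitting alpha between the two tests would not be enough: at 0.025 each, the joint error with no shift is 4.3% to 4.8%, but the time bias in the paired test remains.
3. Restate the power in sections B and C. The 80% applies only to the paired test. Under the assumptions above, the randomised test has about 56% power with 11 per arm and 60% with 12, and 80% would need 19 per arm.
4. Reconcile the thirty-day between-group test in section B with section C, where the parallel placebo comparison runs only from day 14 to day 28.

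Items 1, 2 and 4 are changes of text. Item 3 is the real cost: the sponsor must either accept and disclose lower power for the primary comparison or revisit the sample size.

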Primary measure/platelet aggregation - The primary measurement will be ADP-stimulated platelet aggregation as assessed by the commercially-available VerifyNow P2Y12 assay (Accriva Diagnostics). The assay read-outs are 1) PRU, platelet reactivity units (specific for P2Y12 receptors); 2) BASE, total platelet function despite P2Y12 receptor blockage; and 3) IPA, percent platelet P2Y12 inhibition calculated as  $[(\text{BASE} - \text{PRU}) / \text{BASE}] \times 100$ . Two reports involving patients on antiplatelet therapy with high residual platelet reactivity demonstrated an effect of statins on lowering platelet aggregation via the VerifyNow assay. In CAD patients treated with clopidogrel, the addition of atorvastatin for 30 days resulted in an absolute mean difference of  $102 \pm 54$  PRU compared to baseline, corresponding to a  $37 \pm 14\%$  IPA. In a separate study of CAD/diabetic patients treated with clopidogrel, the addition of atorvastatin for 30 days resulted in an absolute mean difference of  $106 \pm 75$  PRU compared to baseline, corresponding to a  $33 \pm 20\%$  IPA. Similar effect sizes and variabilities of statins on reductions in platelet aggregation were observed in type II

Step	Procedure
1	Venipuncture with G21 butterfly needle.
2	Collect 2 ml blood into sodium citrate tube as waste tube
3	Collect 3x2 mL blood into 3 Greiner Vacuette tubes containing 3.2% sodium citrate. For VerifyNow assays.
4	Collect 2x3 ml blood into 2 Greiner Vacuette tubes containing 3.2% sodium citrate. For platelet activation assays.
5	Collect 1x2 ml blood into Vacuette tube containing EDTA. For CBC assay.
6	Collect 2x2 ml blood for metabolic panel, lipid panel and TSH assays.
7	Collect urine for urinalysis.
8	Pregnancy test with stick assay.

hyperlipidemic patients using light transmittance aggregometry. The relative reductions were reported as  $30 \pm 23\%$  (pravastatin),  $19 \pm 16\%$  (atorvastatin), and  $22 \pm 22\%$  (simvastatin).

[figure not shown]

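### The randomised comparison is an unadjusted t-test with its outcome form, visit and baseline unstated, and patients lost between randomisation and day 28 may be excluded and replaced

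*Combined protocol and SAP*

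**What the plan says.** All references are to the combined protocol and SAP, under the heading Proposed studies.

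- **Section B, primary measure.** The outcome is given as follows: "The primary measurement will be ADP-stimulated platelet aggregation as assessed by the commercially-available VerifyNow P2Y12 assay". The trial is sized on PRU.
- **Section B, tests.** The randomised comparison has one sentence: "Between-group thirty day evolocumab treatment will be tested by standard two-group t-test (two-sided, evolocumab vs vehicle control group run in parallel". A pre-treatment comparator appears only in the sentence on the within-group paired test, "using each subject as its own control (evolocumab treatment vs vehicle pre-treatment control". On timing, the section says "we have revised our experimental design to have a primary endpoint of 30-day treatment".
- **Section C, samples.** "All patients recruited will start with placebo and blood and urine samples will be collected at day 7 and day 14". Patients are then randomised, sampled at days 21 and 28, and all move to evolocumab. Days 7 and 14 are therefore two placebo values taken before randomisation; days 21 and 28 are the only samples in the randomised period.
- **Section C, dropouts.** Data from a patient who drops out may go unused unless they reach at least day 28, and recruitment continues until 22 complete data sets exist.
- **Section F, Analysis.** It states the primary hypothesis for thrombin-peptide stimulation, not ADP. It gives no model, analysis set or missing-data rule.

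**The concern.** There are two separate matters.

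**The form of the test.** The sentence fits at least three analyses: the on-treatment value, the change from a single run-in value, and the change from the mean of both run-in values. The documents do not choose among them, and they do not say whether the pre-treatment control in the paired test is day 7, day 14 or their mean. The readings differ in power, and leaving the choice open allows it to be made after the data are seen. Two pre-randomisation measurements of the outcome are collected but not used as covariates.

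**The analysis set.** Randomisation follows day 14. A patient who is randomised, gives a day-21 sample and leaves before day 28 can be dropped and replaced. If leaving is related to treatment or to response, the arms being compared are no longer those that were randomised. This is a risk of bias, not a loss of precision.

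**Working it through.** **1. The plan's own figure.** A paired t-test with difference 51, SD 54 and two-sided alpha 0.05 (noncentral t) has 80.6% power at n = 11, so the stated 11 reproduces. It is a one-group calculation. The remaining steps concern the two-group comparison.

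**2. Inputs.**
- Difference 51 PRU and change SD 54: section B.
- Raw SD: section B states "The reference range for the VerifyNow assay in individuals not on antiplatelet therapy is 180-376 PRU". Read as a central 95% range (an assumption), SD = (376 − 180)/3.92 = 50.0.
- Correlation r, common to all pairs of visits (an assumption): r = 1 − 54²/(2 × 50²) = 0.417.
- q is the correlation between days 7 and 14; q = r unless stated.
- 12 per arm (24 enrolled) or 11 per arm (22 complete sets).

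**3. SD under each analysis.**
- Change from one run-in value: 54.0
- Raw on-treatment value: 50.0
- Change from the two-visit mean: 50 × √(1 + (1 + q)/2 − 2r) = 46.8
- ANCOVA on the two-visit mean, residual: 50 × √(1 − 2r²/(1 + q)) = 43.4

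**4. Power.** Noncentral t, two-sided 0.05, df = 2n − 2. For ANCOVA, df = 2n − 3 and the variance is multiplied by 1 + 1/(2n − 4).

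| | Change, one value | Raw value | Change, two-visit mean | ANCOVA |
|---|---|---|---|---|
| 12 per arm | 59.9% | 66.6% | 72.4% | 76.3% |
| 11 per arm | 55.9% | 62.4% | 68.2% | 72.0% |
| n per arm for 80% | 19 | 17 | 15 | 13 |

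Simulation of 40,000 trials at 12 per arm gave 60.1%, 66.5%, 72.4% and 76.4%. Simulated false-positive rates under no effect were 4.8% to 5.3% for all methods.

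**5. Sensitivity at 12 per arm.**

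| Assumption | Change, one value | Raw value | Change, two-visit mean | ANCOVA |
|---|---|---|---|---|
| Raw SD 50, r = 0.42, q = 0.7 | 59.9% | 66.6% | 65.9% | 74.1% |
| Change SD 54, r = 0.2 | 59.9% | 79.9% | 72.4% | 80.5% |
| Change SD 54, r = 0.5 | 59.9% | 59.9% | 72.4% | 75.1% |
| Change SD 54, r = 0.7 | 59.9% | 40.3% | 72.4% | 72.7% |
| Change SD 54, r = 0.8 | 59.9% | 28.8% | 72.4% | 71.7% |
| Change SD 75, r = 0.3 | 35.7% | 47.0% | 45.2% | 50.7% |
| Change SD 75, r = 0.8 | 35.7% | 17.2% | 45.2% | 44.6% |

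The rows with change SD held fixed do not use the reference range; raw SD = change SD/√(2(1 − r)), for example 54/√1.6 = 42.7 at r = 0.2. The SD of 75 is from the second study in section B ("In a separate study of CAD/diabetic patients treated with clopidogrel").

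**6. Dropout rule.** No bias figure can be derived. The only allowance is "we estimate that 10% may not be eligible based on exclusion criteria and/or may not return for scheduled blood draws", which mixes ineligibility with non-return. Losses between days 14 and 28 could be zero.

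**The case against.** - **The t-test is valid, so ANCOVA is a preference.** The first part is right. A t-test on change from the two-visit mean would capture most of the gain: ANCOVA adds 4 points at r = 0.42, about nothing at 0.7, and loses 1 at 0.8. Outside the range shown, with change SD held at 54, it trails the raw value by 1.3 points at r = 0.1 (83.0% against 84.3%) and change from the two-visit mean by 1.6 at r = 0.9 (70.8% against 72.4%). The case for ANCOVA is that r is unknown and no single t-test reading is close to best across the range.
- **The text hints at change and at day 28.** Section B speaks of describing reductions, section C of comparing changes, and day 28 is the sample nearest to thirty days. These hints make the raw-value reading less likely, but they define neither form nor baseline. Change from one value against change from the two-visit mean is still 60% against 72%. The study-design figure is not reproduced in the text available and may label visits.
- **The shortfall from 80% is a sample-size problem.** This stands. It comes from sizing on a paired test, and ANCOVA does not cure it in the base case. At the full 102 PRU every option exceeds 99% at 12 per arm, so the choice matters only at the halved effect.
- **r = 0.42 joins two populations.** It does: people off antiplatelet therapy and clopidogrel-treated patients. Hence the sensitivity rows.
- **The dropout wording is permissive and the proposed set is still conditional.** Both are true. Discretion without a rule is part of the problem, and requiring one later sample is a weaker condition than completing to day 28.

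**Conclusion.** The concern holds, as something that should be changed rather than a fatal error, with medium confidence.

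On form, visit and baseline, the plan leaves its one randomised test undefined. In the base case the three readings span about 12 points of power at 12 per arm, and none reaches 80%. ANCOVA on values already collected is the best option or within 1 point of it for correlations from 0.2 to 0.8. These figures apply only if ADP-stimulated PRU is the primary measure, and they rest on a 51 PRU difference, the borrowed SDs and an assumed correlation.

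On the analysis set, the exclusion and replacement rule conditions on events after randomisation. The bias is unquantified and would be nil if nobody leaves between days 14 and 28.

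**What to change.** 1. Reconcile section B (ADP) with section F (thrombin peptide) on the primary measure, and the 30-day treatment endpoint in section B with the section C schedule, where day 28 falls 14 days after randomisation.
2. Replace the two-group t-test with an ANCOVA of the primary platelet measure at the chosen visit (day 28 as designed), adjusted for the mean of the day 7 and day 14 values.
3. Replace the section C exclusion sentence so that every randomised patient with a post-randomisation sample is analysed in the assigned arm. One option is a repeated-measures model on days 21 and 28 with treatment-by-day and baseline-by-day terms, unstructured covariance and Kenward-Roger degrees of freedom. With two visits the covariance has only three parameters. With complete data its day-28 result equals the ANCOVA; on one simulated data set both gave an effect of −35.538 with standard error 15.954.
4. Report by arm anyone randomised with no later sample, and keep the completer analysis as a sensitivity analysis.

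The cost is one degree of freedom, modest extra modelling and revised analysis wording, which should be fixed before unblinding. No new samples or visits are needed.

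### The 80% power holds only for the one-group paired test; at 11 per arm the planned test against placebo has about 56% power for 51 PRU if both arms have SD 54

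*Combined protocol and SAP*

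**What the plan says.** Under Proposed studies, item B (Power Calculation, Primary measure), the plan names two two-sided tests. One is a paired t-test within the evolocumab group. The other compares the arms: "Between-group thirty day evolocumab treatment will be tested by standard two-group t-test". The basis of the sample size is then given: "The sample size estimates have been run using one-group, paired t-test published data".

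A mean difference of 102 PRU with SD 54 yields 6 subjects, and halving the difference to 51 PRU yields 11. The 11 is carried over to the other arm: "An equal number of subjects will be required for the placebo group run in parallel". After an allowance of 10% for ineligibility or missed visits, the paragraph ends: "Thus, for 80% power, the target enrollment is 24 subjects over two years".

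Item C (Study Design) attaches a similar power to a smaller number: "recruitment of total 20 participants into this study will give ~80% power for statistical significance of 0.05". It also says recruitment will continue until 22 subjects have complete data. It presents the placebo comparison as the merit of the design: "The power of this design is that we can compare any changes due to Evolocumab therapy relative to a placebo control".

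On timing, item B says "we have revised our experimental design to have a primary endpoint of 30-day treatment". Item C randomises after the day-14 sample and continues: "Blood and urine samples will be collected at day 21 and day 28. Then, all patients will receive Evolocumab".

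**The concern.** A sample size for a one-group paired test does not transfer to a two-group test when the same number is repeated in a second arm. The difference between two independent means has twice the variance of one mean, so the same effect and SD need nearly twice as many subjects per arm. The plan's 80% is stated for the whole trial, yet the test behind it does not use the placebo arm.

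The randomised contrast is the one that separates a drug effect from time trends and regression to the mean, and the plan presents it as the strength of the design. A reader would take the risk of missing 51 PRU to be 20%. If the risk is much higher, a non-significant placebo comparison could be misread as evidence of no effect. The trial might also come to rest on the uncontrolled within-group change, because the plan does not say which test decides.

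**Working it through.** **Inputs from item B.** Difference δ = 51 PRU (half of 102); SD of change from baseline 54; two-sided alpha 0.05; 11 subjects per arm. Allocation is 1:1 and 22 complete data sets are required (item C).

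**Assumptions, because the plan is silent.** The two-group test compares changes from baseline, the SD of change is 54 on placebo as well, and the mean placebo change is zero.

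**1. Reproduce the plan's figure (paired test).** Noncentrality = (δ/SD)√n, with n − 1 df. δ/SD = 51/54 = 0.944.
- n = 11: 0.944 × √11 = 3.13, 10 df, power **80.6%**. The plan's 11 is confirmed.
- n = 10: 0.944 × √10 = 2.99, 9 df, power 75.7%.
- At 102 PRU, 5 subjects give 87.8%, so the stated 6 is slightly conservative.

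**2. The planned two-group test.** Noncentrality = (δ/SD)√(n/2), with 2n − 2 df, n per arm. At n = 11 this is 0.944 × √5.5 = 2.21.

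| Per arm | Total | Power for 51 PRU |
|---|---|---|
| 10 | 20 | 51.5% |
| 11 | 22 | **55.9%** |
| 12 | 24 | 59.9% |
| 18 | 36 | 78.6% |
| 19 | 38 | 80.9% |

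The 24 row applies only if everyone enrolled is evaluable. The chance of missing 51 PRU at 11 per arm is 100 − 55.9 = 44.1%. The standardised difference detectable with 80% power at 11 per arm is 1.256, or 1.256 × 54 = 67.8 PRU.

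**3. Sensitivity at 11 per arm (assumed values).**
- *Placebo SD of change*, evolocumab SD held at 54, using SD = √[(54² + SD_placebo²)/2]: SD 20 gives 79.8%, 27 gives 76%, 40 gives 67%, 75 gives 41%.
- *Follow-up values instead of changes*, with SD of change fixed at 54, so that the SD of a single value is 54/√[2(1 − ρ)]: ρ = 0.25, 0.5 and 0.75 give SDs of 44.1, 54.0 and 76.4, and power of 73%, 56% and 32%.
- *Baseline-adjusted analysis*, residual SD = that SD × √(1 − ρ²), 19 df: 76%, 68% and 61% for the same ρ.
- *The second VerifyNow study quoted in item B* (106 ± 75), halved the same way to 53 PRU with SD 75: 35% two-group and 56% paired.
- *The unhalved effect*, 102 PRU with SD 54: 98.8% two-group.

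**4. Timing.** Randomisation follows day 14 and the last sample before all patients move to evolocumab is day 28: 28 − 14 = 14 days of randomised treatment. The 102 PRU was observed after 30 days of atorvastatin, and item B chose 30 days because longer statin treatment had shown additional effects. The figures above therefore assume that the 30-day effect is already present at 14 days.

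**The case against.** The strongest reply is that the plan discloses its basis. The paired test is named in the same paragraph as the 80%, the inputs are given, and the 11 reproduces. The fault lies in carrying that number to a second test, not in the calculation. That is fair, but the disclosure does not give the placebo comparison 80% power. The Secondary measures paragraph also claims at least 80% for differences between treatment groups, which encourages a reader to apply the same figure to PRU.

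Second, no placebo-arm SD is given. The 54 comes from clopidogrel-treated patients given atorvastatin and may include variation in drug response that placebo patients would lack. This stands as a limit on the exact 56%. Two-group power does reach 80% at the edges: with a placebo SD of change of about 20 PRU or less, or with follow-up values at a within-subject correlation near 0.1 (81%). The documents support neither. Treating the quoted reference range of 180–376 PRU as a 95% interval (an assumption) gives SD 196/3.92 = 50 and 62% on follow-up values, still well short.

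Third, at 102 PRU the two-group test is amply powered. True, but 51 PRU is the effect the plan chose to set its sample size.

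Fourth, 76% is not far from about 80%, and 22 complete data sets rather than 20 is the operative target. The 20-participant statement is therefore the lesser error.

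Finally, item F names thrombin-peptide activation, not the ADP-stimulated measure, as the primary hypothesis. That inconsistency needs its own resolution. The figures here concern PRU, the only measure for which item B calculates a sample size.

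**Conclusion.** The concern holds. The 80% is right for a paired test in 11 evolocumab subjects and wrong if read as the power of the placebo comparison. For 51 PRU at 11 evaluable per arm, the two-group test has about 56% power, conditional on changes being compared, SD of change 54 in both arms and no mean placebo change. Over placebo SDs of 27 to 75 the figure runs from 76% down to 41%, and the other analyses tried at correlations of 0.25 to 0.75 also stay below 80%.

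The statement for 20 participants is unsupported on either test (76% paired, 52% between groups). The paired figure needs no placebo assumption. All of these figures further depend on an effect observed at 30 days being present 14 days after randomisation. The text should be corrected before the power statement is relied on.

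**What to change.** 1. Name the randomised between-group comparison as the confirmatory test and label the within-group paired test supportive. This fits the stated aim of a randomised, double-blind assessment.
2. In items B and C, say that 80% refers to the paired test with 11 subjects. Beside it, give the between-group figure at 11 evaluable per arm: about 56% for 51 PRU, or 80% for about 68 PRU, with the SD assumption stated.
3. State whether the two-group test uses changes, follow-up values or a baseline-adjusted model.
4. Remove or correct the 20-participant statement, and keep 22 evaluable and 24 enrolled as distinct figures.
5. Reconcile the 30-day endpoint in item B with the day-28 sample in item C, and state that the power is conditional on the effect being present by that sample.

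The cost is text only, with no extra patients. The sponsor would be acknowledging openly that the randomised contrast is underpowered for 51 PRU. If 80% for that contrast is wanted instead, the same assumptions imply 38 evaluable subjects, or 38/0.9 = 42.2, so 43 enrolled.
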